addition of evolocumab in patients treated with moderate or high intensity statin therapy resulted in greater decrease in percent atheroma volume (PAV) assessed by intravascular ultrasound (IVUS) during 18 month of therapy (12), while there was no plaque regression observed in patients treated with statins alone. Reduction in the atherosclerotic disease burden, atheroma (PAV) was observed in 67% of the evolocumab and 47% of the placebo group regardless of baseline LDL-C levels.

One-third of the patients treated with evolocumab and almost half of statin-treated patients from the GLAGOV trial did not demonstrate plaque volume reduction despite the significant lipid reduction suggesting that different mechanisms might be responsible for lesion regression in a subgroup of patients, and these patients might require different treatment approach. Another possibility is that beneficial changes in lesion morphology were not captured in the study due to inherent limitations of IVUS. Optical coherence tomography (OCT) provides high-resolution (10-20 µm) in vivo images of plaque morphology and is the only currently available intravascular imaging modality capable of the assessment of the fibrous cap thickness in vivo (13,14). The presence of a thin fibrous cap overlying a large necrotic core is the hallmark of high-risk vulnerable plaques (14,15). While intravascular ultrasound (IVUS) lacks the spatial resolution to accurately access the changes in fibrous cap thickness (FCT), OCT's superior image resolution allows the accurate detection of thin cap fibroatheroma (TCFA) and estimate the effect of various lipid-lowering therapies on FCT (16-18). The aim of the ongoing HUYGENS study is to evaluate the effect of evolocumab combined with maximally tolerated statin therapy on

OCT defined FCT in subjects with non-ST-elevation acute coronary syndrome (NSTE-ACS).

Near-infrared spectroscopy (NIRS) detects the lipid (cholesterol) content of atherosclerotic plaques by generating lesion "chemogram" and calculating lipid core burden index (LCBI) characterizing the amount of lipid on a 0 to 1000 scale. Large lipid-core plaques (LCP) detected by NIRS have been shown to be a signature of plaques causing STEMI and are associated with a high risk of periprocedural MI (19,20).

Results of YELLOW I and II. In a series of YELLOW trials, we investigated the effect of statins on high-risk lipid-rich coronary plaques using intravascular imaging in patients with stable CAD. The aim of our first YELLOW (Reduction in Coronary Yellow Plaque, Lipids and Vascular Inflammation by Aggressive Lipid Lowering) trial was to explore whether these benefits are attributable to reduction in plaque lipid content in obstructive coronary lesions (21). In the study, we randomized 87 patients with multivessel CAD to intensive (rosuvastatin 40 mg daily) or standard-of-care lipid-lowering therapy. Patients underwent PCI for the culprit lesion at the baseline, while obstructive nontarget lesion (NTL) was treated at the staged procedure, follow-up. The inclusion criterion for the trial was FFR less or equal 0.8. NTLs were evaluated at baseline and after 7 weeks of therapy with NIRS and IVUS. The primary endpoint was the change in lipid-core burden index at the 4-mm maximal segment (maxLCBI4mm). Upon follow-up, median reduction in maxLCBI4mm was significantly greater in the intensive versus standard group suggesting that short-term intensive statin therapy may reduce lipid content in obstructive lesions.

In our subsequent YELLOW II study, all patients with obstructive NTL received high-dose statin therapy for 8-12 weeks (22). The aim of the study was to characterize the relationship between the changes in plaque morphology assessed by NIRS/IVUS and OCT, HDL functionality and gene expression in peripheral blood mononuclear cells (PBMC) using microarray analysis. At the follow-up, we observed a significant increase in fibrous cap thickness (FCT) in the study lesion, enhancement of cholesterol efflux capacity (CEC) and significant perturbations of PBMC transcriptome in patients with stable coronary artery disease (CAD) treated with 40 mg rosuvastatin for 8-12 weeks. As a result, the prevalence of TCFA reduced from 20 to 7% (P=0.003) and there was a significant independent association between the thickening of the fibrous cap and improved CEC independent of lipid lowering and CRP reduction. In addition, we observed significant transcriptomic perturbations in genes related to cholesterol synthesis, regulation of fatty acid unsaturation, cellular cholesterol uptake, efflux and inflammation suggesting that several independent molecular mechanisms might be responsible for the beneficial effects of statin on plaque morphology. The unique translational combination of multi-modality intravascular imaging with clinically relevant cellular biology and comprehensive transcriptomics represents a powerful approach to assessing the effects and mechanisms of the efficacy of different lipid-lowering therapies for stabilizing atherosclerotic plaques.

With OCT imaging, we observed an increase in FCT after intensive statin therapy only in a subset of the study patients. Traditionally, response to statins is measured by the changes in serum lipids, however, these changes do not predict the beneficial changes in FCT, therefore, it is important to distinguish statin responders from non-responders using non-invasive methods. In our recent analysis, YELLOW II transcriptomic data was used to predict whether a patient's FCT increased in response to statin therapy using machine learning models (23). One of the model used 18 genes and was able identify statin responders with an accuracy of 95.7%, sensitivity of 94.3% and specificity of 97.1%.

Hypothesis. In the YELLOW III study, we hypothesize that LDL-C lowering with evolocumab 140 mg every 2 weeks will result in a significant increase in OCT-defined minimal FCT and reduction of plaque lipid content assessed by NIRS compared to baseline in patients with CAD undergoing percutaneous coronary intervention (PCI). In addition, we hypothesize that there is an association between the changes in patient's plaque characteristics and PBMC gene expression and lipid metabolites at the baseline, which would allow us to develop a predictive model for detecting subjects that demonstrate the greatest response regarding plaque morphology to PCSK9 inhibition therapy. YELLOW III will provide an additional contribution to the ongoing HYUGENS study due to its unique design combining intravascular imaging and transcriptomic based machine learning approach, which will allow to uncover molecular mechanisms responsible for the beneficial changes in atherosclerotic lesions of patients treated with evolocumab.

STUDY OBJECTIVES

The aim of the study is to assess the effect of evolocumab on coronary plaque morphology using intravascular imaging, NIRS/IVUS and OCT, and PBMC gene expression analysis in patients with stable CAD on maximally tolerated statin therapy.

Primary endpoints. The primary end-points are the changes from baseline to follow-up (follow-up value minus baseline value) in (1) the minimal FCT assessed by OCT and (2) NIRS maxLCBI4mm after 26 weeks of evolocumab.

Secondary endpoints. The secondary endpoints are the changes in (1) the maximal lipid arc, lipid length, lipid volume index, macrophage accumulation and calcification by OCT; (2) PAV and TAV defined by IVUS and (3) PBMC gene expression. In recognition of the role of lipids in CAD and atherosclerosis, we will perform lipidomics to analyze lipid metabolites and lipid derivatives in blood plasma and serum in order to identify CAD biomarkers. Measuring lipid metabolites (and their effectors) might directly lead to the identification pathways of lipid action or lipid metabolism in patients receiving treatment. We will also perform Mass Cytometry (CyTOF) of PBMC to characterize the immune profile and responses in patients receiving a combination of evolocumab plus statin with an eye on identifying biomarkers for detecting and/or predicting favorable changes in plaque morphology as a result of PCSK9 inhibition therapy. Other parameters including the levels of CRP, resistin, adiponectin, perilipin and Lp(a) will also be measured for the same purpose.

Exploratory endpoints. Major Adverse Cardiac Events (MACE) will be defined as a combined clinical endpoint of death, MI (Q wave or non Q-wave with CK-MB >3 times above the upper normal limit (48 U/L), urgent revascularization or stroke at 30 days and 1 year.

STUDY PROCEDURES

This is a single center single arm study, which will be performed in the Cardiac Catheterization laboratory of the Mount Sinai Hospital, New York, NY. After informed consent, patients undergoing clinically indicated elective PCI with a non-obstructive lesion and optimal background statin therapy will be eligible for screening (Figure 1). Non-obstructive lesions (30-50% stenosis) identified by angiography in a non-culprit vessel with lipid-rich plaque will be studied. Subjects will receive evolocumab 140 mg subcutaneously every 2 weeks for 26 weeks. Serial NIRS/IVUS and OCT imaging will be performed in the non- obstructive lesions, first during PCI and subsequently after 26 weeks.

 Screening. Written informed consent must be obtained from all subjects before any study-specific procedures are performed. We will screen patients scheduled for elective coronary angiography and/or coronary artery stenting, who are receiving statin therapy for at least 4 weeks or with history of statin intolerance (should not exceed 20% of the total cohort) with acceptable LDL-C levels. Patients with nonobstructive lesion (30-50% stenosis) by angiography and lipid-rich plaque with lipid arc >90° and minimal fibrous cap thickness ≤ 120 µm detected by OCT will comprise the final study population. Women of childbearing potential will undergo urine pregnancy testing. If necessary, we may request serum pregnancy testing to confirm equivocal urine-based results.

- 2. PCI and baseline imaging. Culprit vessel PCI will be performed according to best current practice. During the same angiographic procedure baseline OCT and NIRS/IVUS imaging of the non-obstructive study lesion will be performed after administration of intra-coronary NTG. A total of 25ml of blood will be drawn from the sheath during angiography for transcriptomic profiling of PBMC (mRNA and miRNA), lipidomics and cytokine analyses. Patients will undergo assessment of lipid levels, CK-MB, Troponin I, liver function, CBC, and hsCRP.
- 3. **Study drug allocation.** All patients will receive subcutaneously administered evolocumab 140 mg every 2 weeks for 26 weeks in addition to statins. Evolocumab will be administered on day 1 (the day of the first treatment) and through week 26 with a personal injector or prefilled auto injector/pens.
- Clinical visits. Study visits will occur during screening (day 1), weeks 12 and 26 (time of follow-up procedure). Subjects must fast overnight when fasting lipid samples are to be obtained.
- 5. Follow up Procedure. The follow-up procedure will be scheduled 26 weeks after the baseline PCI and should occur within ±2 weeks of their specified date. First, routine angiography to check the previous stent will be performed, then, repeat NIRS/IVUS and OCT of the non-obstructive study lesion will be performed after administration of intra-coronary nitroglycerin. A total of 25ml of blood will be drawn

from the sheath during angiography for transcriptomic profiling of PBMC (mRNA and miRNA), lipidomics and cytokine analyses.. All study patients will undergo repeat assessment of lipid levels, CK-MB, Troponin I, liver function, CBC, and hsCRP. Bivalirudin or Heparin will be used as anticoagulation as per standard PCI protocol. All patients will have repeat CK-MB and TnI levels measured at 6-8 hours and if in hospital, 16-24 hours post PCI, and thereafter if levels continue to rise

- 6. Post Follow-up. After the follow up procedure patients will be referred back to their primary care physician as is our usual practice. All further adjustment of lipid lowering and other medications will be at the discretion of the primary care physician. The treatment received after 26 weeks of evolocumab will be documented, and clinical telephone follow up will be performed at 30 days, 6 months and 1 year after the follow-up procedure
- 7. Data analysis. Off-line image analysis will be performed by the Mount Sinai Intravascular Imaging core laboratory, which will have no knowledge of patient clinical presentation and treatment.. Statistical and bioinformatics analyses will be performed by an independent biostatistician unaware of clinical data.

For predictive model construction, each patient will be identified as an evolocumab responder or non-responder depending on whether FCT increased or decreased after the treatment. Similar to our YELLOW II transcriptomic sub study (23), an elastic net regularized generalized linear model and K top scoring pair (KTSP) classifier model will be built using clinical variables and PBMC transcriptomic, lipidomics and cytokine analyses data to predict changes in FCT to ascertain whether a patient's FCT will increase in response to treatment. The transcriptomic data will be pre-processed to identify the

mechanism of missing data, and data imputations will be performed for non-ignorable missing data. The accuracy, sensitivity and specificity of both algorithms will be evaluated in order to select the highest performing model. We believe that the predictive model might allow patients to have their FCT response approximated without undergoing intravascular imaging.

8. Safety reporting. Subjects will be carefully monitored during the study for possible Adverse Events (AEs) from the time of enrollment to the completion of their participation in the study. All adverse events will be fully investigated by the Principal Investigator, classified according to the current definitions of the International Organization for Standardization (ISO) and reported to the Mount Sinai Hospital IRB and Amgen Safety. Timeframes for submission of safety data and aggregate reports to Amgen are described in Tables 1 and 2.

In addition, an independent data and safety monitoring board (DSMB), comprising 3 cardiologists with extensive clinical research experience will oversee this study. The DSMB will be informed within 24 hours of all major adverse events (MACE) defined as a combined clinical endpoint of death, MI (Q wave or non Q-wave with CK-MB >3 times above the upper normal limit (48 U/L), urgent revascularization or stroke at 30 days and 1 year. All minor adverse events will be reported to the DSMB within 5 working days of knowledge of the event. The DSMB will convene after 30, 70 and 110 patients have completed the final procedure and at study closure. The DSMB will have complete discretion to adjudicate all events (major and minor), and, after fair deliberation and at any stage of the trial, to recommend the termination of the study, for whatever reason as they see fit insofar as it may pertain to adverse event occurrence(s). If the DSMB is to recommend termination of the study, the investigators will be given a single opportunity to respond to any concerns the DSMB may raise. After final consideration, if the DSMB again recommends termination of the study, then the study will be terminated. The DSMB may only terminate the study on the basis of MACE and adverse events.

9. Institutional Review Board (IRB). Prior to study initiation and when amended, the study protocol and will be submitted for review and approval to the Icahn School of Medicine at Mount Sinai IRB. Site personnel must provide reports of the progress, or completion, termination or discontinuation of the study to the institutional IRB at appropriate intervals. The primary investigator will verify that each subject has consented, in writing, to direct access to his/her original medical records for trial-related monitoring, audit, IRB/IEC review, and regulatory inspection

Inclusion criteria:

- Men or women aged 18 years or older at screening who signed written Informed Consent
- Patients with coronary artery disease undergoing cardiac catheterization and PCI for a culprit lesion, who also have a non-obstructive study lesion (30-50% stenosis) identified by angiography in a non-culprit vessel.
- Patients with non-obstructive coronary artery disease and a 30-50% lesion identified by angiography
- Patients who are not candidates for PCI or CABG over the next 12 months, in the opinion of the investigator
- Patients treated with statins for at least 4 weeks with LDL-C level ≥ 80 mg/dL for low- or moderate -intensity statin use and ≥ 60 mg/dL for high-dose statin at screening (Table 3). Patients with history of statin intolerance and LDL-C ≥ 100 mg/dL.

- Angiographic criteria: 30-50% reduction of lumen diameter in addition to the target study lesion. The study segment should not have a history of percutaneous coronary intervention (PCI) or coronary artery bypass grafting (CABG), and may not be a bypass graft.
- OCT criteria: study lesion should have a lipid-rich plaque with lipid arc >90° and fibrous cap thickness ≤120 µm.
- Women of childbearing potential must agree to be on an acceptable method of birth control/contraceptive

Exclusion criteria:

- Patients who have acute myocardial infarction (Q wave or non-Q wave with CK-MB > 5 times above the upper normal (31.5 ng/ml) within 72 hours)
- Patients who are in cardiogenic shock
- Patients with left main disease or patients requiring coronary artery bypass graft surgery
- Patients with elevated CK-MB (>6.3 ng/ml) or Tnl (>0.5 ng/ml)
- Patients with platelet count < 100,000 cell/mm³
- Patients who have co-morbidity which reduces life expectancy to one year
- Patients who are currently participating in another investigational drug/device study
- Patients with liver disease
- Patient with creatinine > 2.0 mg/dL
- Pregnant women and women of childbearing potential who intend to have children during the duration of the trial
- Patients having undergone heart transplantation, or those that may undergo heart transplantation during the study period
- Patients with active autoimmune disease

Table 1. Timeframes for submission of safety data and aggregate reports to

Amgen

Safety Data	Timeframe for submission to	Send to
	Amgen	
Suspected Unexpected Serious	At time of regulatory submission	Amgen Safety
Adverse Reaction (SUSARs)		
Pregnancy/Lactation exposure	Within 1 business day of Sponsor	Amgen Safety
and any associated	awareness, for reports meeting serious	
reports/outcomes (i.e.	criteria	
unexpected pregnancy,	Not to evened 15 colorder days of	
pregnancy of partner,	Not to exceed 15 calendar days of Sponsor awareness, for non-serious	
spontaneous abortion,		
congenital anomaly etc.)	reports	
Listing for Safety data	Once per year and at the end of the	NASCR Manager
reconciliationa ^a	study	
Annual Safety Report		
(US IND Annual Report)	Annually	NASCR Manager
Other aggregate analyses	At the time of Sponsor submission to	NASCR Manager
(any report containing Safety data generated during the course of the study)	any body governing research conduct (eg. RA, IRB etc.)	
Final (End of Study Report,		
including):		
	At the time of Sponsor submission to	NASCR Manager
Unblinding data for blinded	any body governing research conduct	
studies	(eg. RA, IRB etc.) but no later than 1	
 Reports of unauthorized use of a marketed product 	calendar year of study completion	

^a Listing for reconciliation should include all ICSRs submitted to Amgen Safety per contract

Table 2. Timeframes for submission of safety data and aggregate reports to Amgen

- Device related adverse events for studies using Amgen devices^a and Product

complaints

Safety Data	Timeframe for submission to Amgen	Send to
Serious Adverse Device Effect ^b (SADE)	Within 1 business day of Sponsor awareness	Amgen Safety
Adverse Device Effect (ADE)	Not to exceed 15 calendar days of Sponsor awareness	Amgen Safety
Product Complaint ^c	Immediately, not to exceed 1 business day of Sponsor awareness	Amgen Quality

^a Refer to local Safety representative (LSO) to clarify reporting requirements for the Amgen device per regulations in the country where the study is being conducted.

^b Adverse device effect is: any adverse event related to the use of a medical device. Adverse device effects include adverse events resulting from insufficient or inadequate instructions for use, adverse events resulting from any malfunction of the device, or adverse events resulting from use error or from intentional misuse of the device.

^c Product Complaint is: Any written, electronic or oral communication that alleges deficiencies related to the identity, quality, durability, reliability, safety, effectiveness, or performance of a drug, combination product, or device after it is released for distribution to market or clinic by either: (1) Amgen or (2) distributors or partners for whom Amgen manufactures the material. This includes all components distributed with the drug, such as packaging, drug containers, delivery system, labelling, and inserts. Examples include:

- Device that is damaged or broken
- Bent or blunt needles
- Missing or illegible labeling
- Inability of customer to administer the product
- Product with an unexpected color, appearance, or particles

• User error (i.e, an act or omission of an act that results in a different combination product or medical device response than intended by the manufacturer or expected by the user, where the user attempted to use the combination product or medical device in good faith and experienced difficulty or deficiency administering the product).

[figure not shown]
Reports of misuse of a combination product or medical device (i.e, the intentional and improper use of a combination product or medical device not in accordance with the authorized product information) are not considered Product Complaints.

Table 3. High-, Moderate-, and Low-Intensity Statin Therapy*

High-Intensity Statin Therapy	Moderate- and low- intensity statin therapy
Atorvastatin ≥40 mg	Atorvastatin <40 mg
Rosuvastatin ≥20 mg	Rosuvastatin <20 mg
	Simvastatin < 80 mg
	Pravastatin ≤ 80 mg
	Lovastatin ≤ 40 mg
	Fluvastatin ≤ 80 mg
	Pitavastatin ≤ 4 mg

Stone et al. 2014 2013 ACC/AHA Blood Cholesterol Guideline on the Treatment of Blood Cholesterol to

Reduce Atherosclerotic Cardiovascular Risk in Adults. JACC Vol. 63, No. 25, 63(25 Pt B):2889-934.

ACS – acute coronary syndrome; LCBI – lipid core burden index; OCT – optical coherence tomography; PAV=percent atheroma volume; SC – subcutaneously; TAV=total atheroma volume; FCT – fibrous cap thickness; PBMC - peripheral blood mononuclear cell

17

References:

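### The response models use FCT change or its sign, which contains baseline FCT, and nothing conditions on or benchmarks against it, so markers of the starting cap can pass for markers of response to PCSK9 inhibition

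*Combined protocol and SAP*

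**What the plan says.** - **Association.** Hypothesis expects a link between changes in a patient's "plaque characteristics and PBMC gene expression and lipid metabolites at the baseline, which would allow us to develop a predictive model".
- **Outcome.** Primary endpoints defines "changes from baseline to follow-up (follow-up value minus baseline value) in (1) the minimal FCT assessed by OCT".
- **Responder label.** Study Procedures item 7 (Data analysis) states that "each patient will be identified as an evolocumab responder or non-responder depending on whether FCT increased or decreased after the treatment". No minimum change is set and the starting value plays no part.
- **Predictors.** The same item plans an elastic net and a K top scoring pair (KTSP) classifier using "clinical variables and PBMC transcriptomic, lipidomics and cytokine analyses data to predict changes in FCT". The clinical variables are not listed. Item 2 draws the blood during the procedure at which baseline OCT is done.
- **Purpose.** Data analysis hopes the model will allow "patients to have their FCT response approximated without undergoing intravascular imaging". Hypothesis goes further: it speaks of response to PCSK9 inhibition and of uncovering the molecular mechanisms behind plaque improvement. Secondary endpoints repeats the attribution to PCSK9 inhibition.
- **Design.** Screening requires "minimal fibrous cap thickness ≤ 120 µm detected by OCT", and Study Procedures describes a single-arm study.

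The supplied text nowhere names baseline FCT as a covariate, stratifier or benchmark for these analyses.

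**The concern.** Baseline FCT enters the change score with a minus sign. Unless follow-up FCT moves one-for-one with measured baseline FCT, patients who start thin tend to gain more, partly through regression to the mean. Patients are selected for thin caps and there is no control arm, so the design cannot separate this tendency from a drug effect.

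A transcript or lipid that only reflects how thin the cap was on the day of sampling can therefore be associated with the change, or with the responder label, while saying nothing about who responds given the starting cap. If such a marker is then presented as a mechanism of evolocumab or a marker of PCSK9 response, the conclusion is wrong. Without a baseline-FCT benchmark, the reader cannot tell whether a blood model knows anything beyond starting thickness.

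**Working it through.** The supplied text gives no sample size, SD, effect size or tracking correlation, so there is no plan figure to reproduce. All inputs below are assumptions except the 120 µm entry limit. The number 110 is the last interim count for data and safety monitoring board meetings in item 8 (Safety reporting), used as an assumed n.

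**1. Closed form, ignoring the entry limit.** Let Y0 and Y1 be baseline and follow-up FCT with equal SD and correlation ρ, and D = Y1 − Y0. Then cov(Y0, D) = −σ²(1 − ρ) and var(D) = 2σ²(1 − ρ), so corr(Y0, D) = −√((1 − ρ)/2). A marker with correlation r to a thin baseline cap, and no link to Y1 beyond Y0, has corr(marker, D) = r√((1 − ρ)/2).

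Example: ρ = 0.5, r = 0.3 gives 0.3 × 0.5 = 0.15. By Fisher's z with n = 110, the chance of two-sided p < 0.05 is Φ(0.1511 × √107 − 1.960) = Φ(−0.397) = 0.35.

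| ρ | r = 0.2 | r = 0.3 | r = 0.5 |
|---|---|---|---|
| 0.3 | 23% | 46% | 88% |
| 0.5 | 18% | 35% | 75% |
| 0.7 | 13% | 23% | 53% |
| 0.9 | 8% | 11% | 21% |

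At n = 70, ρ = 0.5 and r = 0.5 gives 55%.

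**2. With the entry limit.** Baseline has mean 95 and SD 20 µm before the cut at 120 µm, the mean rise is 15 µm, and n = 110. In the r columns, the first figure sets the marker correlation before the cut and the second among enrolled patients.

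| ρ | FCT increased | corr(Y0, D) | AUC, baseline FCT alone | p < 0.05 for change, r = 0.3 | p < 0.05 for change, r = 0.4 | AUC, one null marker |
|---|---|---|---|---|---|---|
| 0.3 | 79% | −0.52 | 0.75 | 29% / 37% | 47% / 60% | 0.56–0.60 |
| 0.5 | 81% | −0.44 | 0.71 | 21% / 28% | 35% / 45% | 0.55–0.58 |
| 0.7 | 86% | −0.33 | 0.66 | 14% / 18% | 22% / 28% | 0.54–0.56 |

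For the responder label, 1,500 simulated studies per setting (correlation set before the cut) gave 9–15% at r = 0.3 and 10–22% at r = 0.4. With baseline FCT in the model the false-positive rate was 4–6%.

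**3. With OCT measurement error.** Screened mean 120, SD 40 µm, kept if observed FCT is above 30 and at most 120 µm. True gain 20, residual SD 20, r = 0.4 among enrolled, n = 110. Slope is that of true follow-up on true baseline. Each result is the correlation of a thin-cap marker with change, and the chance of p < 0.05.

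| Slope | Reliability | Marker tracks | Unadjusted | Adjusted for observed baseline |
|---|---|---|---|---|
| 1.0 | 1.0 | either | 0.00, 5% | 0.00, 5% |
| 0.5 | 1.0 | either | 0.19, 51% | 0.00, 5% |
| 0.7 | 0.8 | observed cap | 0.12, 25% | 0.00, 5% |
| 0.7 | 0.8 | true cap | −0.01, 5% | −0.11, 20% |
| 0.5 | 0.8 | true cap | 0.05, 8% | −0.08, 13% |
| 1.0 | 0.8 | true cap | −0.10, 18% | −0.15, 33% |
| 1.0 | 0.6 | true cap | −0.12, 24% | −0.18, 46% |

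Adjustment restores 5% when the marker tracks the measured baseline. When it tracks the true cap and OCT is noisy, adjustment raises the false-positive rate, with the association pointing the other way from the one expected.

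**The case against.** Several stronger readings are tempting, and the documents do not support them.

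- **Every thin-cap marker will look like a predictor.** Even at r = 0.3, section 2 of the working flags most such markers in fewer than half of studies. With slope 1 and no error the effect vanishes, and with measurement error a marker of the true cap can point to non-response.
- **The plan has decided against adjustment.** It is silent. The clinical variables are unlisted, so baseline FCT is not excluded, although the aim of avoiding imaging makes it an unlikely input. The sentence in Hypothesis is not an analysis specification, and part of the document was not supplied.
- **The prediction model is invalid.** The stated task is "to predict changes in FCT to ascertain whether a patient's FCT will increase in response to treatment". A blood marker that forecasts an increase because it reflects a thin cap serves that task.
- **A null blood model would discriminate as well as baseline FCT.** The AUC of 0.66–0.75 belongs to baseline FCT itself. One null marker reaches 0.54–0.60, and no multi-marker model was simulated. Data analysis plans accuracy, sensitivity and specificity, not marker-by-marker tests at 5%, so the rates above illustrate the mechanism rather than forecast the model's error.
- **Adjustment is a cure, or should replace the planned models.** Section 3 shows it is no general cure. A mandatory baseline OCT covariate would defeat the imaging-free purpose. A KTSP label based on residuals would change the target: residuals average zero, so about half of patients become non-responders, whereas 79–86% have an increase in section 2.

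These points limit the claim. They do not answer the absence of any benchmark or conditional analysis behind the statements on mechanism and drug response.

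**Conclusion.** The concern holds in a limited form. Change and its sign contain baseline FCT, and no supplied text conditions on it or benchmarks against it, so blood markers correlated with the starting cap can appear to predict response. Imaging-free prediction stands. What is not supported is reading selected markers as mechanisms of, or response to, PCSK9 inhibition.

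Under the section 2 assumptions the chance of a misleading association with change is about 14–60% for a marker correlated 0.3–0.4 with baseline FCT. Over the whole closed-form grid at n = 110 it runs from 8% to 88%, and it falls to the nominal 5% when follow-up tracks baseline with slope 1 and no error. All of this rests on assumed n, SDs and correlations. The mean FCT change is not at issue here.

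**What to change.** In Study Procedures item 7 (Data analysis), keep the raw-change elastic net and KTSP models for imaging-free prediction, list the clinical variables, and add:

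1. The performance of baseline minimal FCT alone, and the increment from blood markers over it, assessed with the same validation as the main models.
2. For any claim about response or mechanism, the association of each selected marker with week-26 minimal FCT adjusted for baseline minimal FCT, beside the unadjusted result.
3. A sensitivity analysis of item 2 over an assumed range of OCT FCT reliability (for example 0.6 to 1.0, as in the working), correcting for error in the baseline value.
4. A rule for interpretation: call a marker one of response or mechanism only if it holds with the same sign in both analyses, survives the reliability range and adds to baseline FCT. Agreement of the two analyses is not enough alone: with slope 1 and reliability 0.8, both were biased in the same direction.

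Baseline FCT is already measured in every patient as an entry criterion, so the cost is wording and a little more analysis. The downside is that some markers may lose their response interpretation.
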